#### 2.9.4. Other Variables

Other assessments are:

- A single blood sample for Apolipoprotein E gene (*ApoE*) obtained from subjects who provide legally acceptable informed consent, collected at any time after eligibility for randomization and continued participation in the study has been confirmed but prior to Week 52.
- Other biomarkers will be analyzed as well. Their analysis is pre-specified in the separate Research Plan “TRx-237-039\_Secondary Research Plan\_Plasma Biomarker Analysis\_v2.2\_16Mar23”. The analysis to be performed is described in more detail in Section 7 of this SAP.
- MRI arterial spin labelling parameters will be provided in a subject data listing.

Sponsor:	TauRx Therapeutics Ltd.		
Protocol:	TRx-237-039		
Document Version No.:	3.0	Document Date:	07-JUN-2023

### 3. SUBJECT POPULATIONS

#### 3.1. Population Definitions

The following subject populations will be evaluated and used for presentation and analysis of the data.

##### 3.1.1. Double-Blind Populations

**Intention-to-Treat (ITT) Population:** all randomized subjects. Subjects are analyzed as randomized.

**Efficacy Modified Intention-to-Treat (E-MITT) Population:** all ITT subjects who received at least one dose of study drug and have a Baseline and at least one *valid* post-Baseline efficacy assessment (either ADAS-cog11 or ADCS-ADL23). Subjects are analyzed as randomized.

**MRI Imaging Modified Intention-to-Treat (MI-MITT) Population:** all ITT subjects who received at least one dose of study drug and have a Baseline and at least one *valid* post-Baseline volumetric MRI (either whole brain or temporoparietal lobe). Subjects are analyzed as randomized.

**PET Imaging Modified Intention-to-Treat (PI-MITT) Population:** all ITT subjects with screening CDR of 0.5 and who received at least one dose of study drug and have a Baseline and at least one *valid* post-Baseline SUVR assessment (temporal lobe). If data is available from subjects with a CDR > 0.5, these subjects will not be included in this population. Subjects are analyzed as randomized.

**Per Protocol (PP) Population:** all subjects who are in the E-MITT and MI-MITT population, without any important protocol deviation (see Section 3.2) that would deem the subject exclusionary from the PP Population (as per BDRM decision) or intercurrent medical events that could confound the interpretations. Subjects are analyzed as randomized. **Important here refers to a classification that is decided during BDRM based on the original protocol deviation classification as major/minor and their impact on key (efficacy/safety) outcomes of this study. The original classification as major/minor will be provided as well.**

A valid value means that the assessment was not affected by prior initiation of an AChEI and/or memantine.

**Safety Population:** all subjects who received at least one dose of study drug. Subjects are analyzed as treated. If a subject received different doses, the predominant treatment group (based on the number of doses) will be assigned.

**v5-Populations:** If the above-mentioned populations (ITT, E-MITT, MI-MITT, PI-MITT, PP, Safety) are restricted to subjects randomized under study protocol version 5.0 or higher, which are the primary efficacy analysis populations, the population names are: ITTv5, E-MITTv5, MI-MITTv5, PI-MITTv5, PPv5, and Safetyv5.

**Pharmacokinetic (PK) Population:** all subjects who were administered at least one dose of study drug and have at least one analyzable post-dose PK sample.

Sponsor:	TauRx Therapeutics Ltd.		
Protocol:	TRx-237-039		
Document Version No.:	3.0	Document Date:	07-JUN-2023

The analysis of estimands is based on the ITT population. For the FDA, the modified endpoint specific ITT populations (MITTs) will be analyzed. The Safety population is the primary population for the analysis of safety endpoints.

Two population trackers will be generated and will be provided to Cytel for the use in the analyses. The first as a result of the double-blind treatment phase BDRM, and the second as a result of the open-label treatment phase Data Review Meeting (DRM). These trackers will specify if subjects are included or need to be excluded from certain populations (e.g., TOTOS, PP, PP-OL). The population tracker from the BDRM will also specify if dropouts are potentially related to treatment.

### 3.1.2. Open-Label Populations

The following subject populations will be evaluated and used for presentation and analysis of the open-label data:

**Intention-to-Treat Open-Label (ITT-OL) Population:** all randomized subjects who received at least one dose of study drug from the open-label treatment phase or continued off-treatment during the open-label treatment phase (e.g., TOTOS subjects from the double-blind treatment phase). Subjects are analyzed as randomized.

**Per Protocol Open-Label (PP-OL) Population:** all randomized subjects who received at least one dose of study drug from the open-label treatment phase and without any important protocol deviation during the open-label treatment phase. Subjects are analyzed as randomized.

**Safety Open-Label (Safety-OL) Population:** all subjects who received at least one dose of study drug from the open-label treatment phase. Subjects are analyzed as treated.

**Pharmacokinetic Open-Label (PK-OL) Population:** all subjects who were administered at least one dose of study drug from the open-label treatment phase and have a subsequent analyzable open-label treatment phase PK sample.

**v5-Populations:** If the above-mentioned populations (e.g., ITT, and PP) are restricted to subjects randomized under study protocol version 5.0 or higher, which are the primary efficacy analysis populations, the population names are: ITTv5-OL, and PPv5-OL.

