### 17.3 Analysis Populations

The following subject populations will be used for the statistical analyses; all definitions reply on the treatment period in the double-blind phase excluding open-label assessments (population definitions will be used for the delayed-start analyses without any modifications):

- Intent-to-Treat (ITT) population will include all randomized subjects. Three subsets are defined as follows:
  - The Efficacy Modified Intent-to-Treat (E-MITT) population will include all randomized subjects who take at least one dose of the study drug and have a baseline and at least one valid post-baseline efficacy assessment in the treatment period (prior to any potential follow-up assessment).
  - An MRI Imaging Modified Intent-to-Treat (MI-MITT) population will include all randomized subjects who took at least one dose of study drug and have at least one valid baseline and at least one valid post-baseline volumetric MRI.
  - The Imaging Modified Intent-to-Treat population (PI-MITT) for F-FDG-PET will include all randomized subjects with screening CDR 0.5 who took at least one dose of study drug and have a baseline and a valid post-baseline SUVR assessment.
- The Per Protocol (PP) population will include all subjects who are in the E-MITT and MI-MITT populations and who do not have any PP exclusionary protocol deviations or intercurrent medical events that could confound the interpretations. PP exclusionary deviations, irrespective of their classification as minor/major, and intercurrent medical events will be determined prior to treatment unblinding.
- The Safety population will include all randomized subjects who take at least one dose of study drug.

Due to the introduction of MTC spiking in the placebo arm with Protocol Version 5.0, the respective MITT populations will be restricted to subjects randomized to Protocol Versions 5.0 and above for the primary and key secondary analyses as per the SAP. The full MITT populations will be analyzed for these as a sensitivity analysis. Details will be provided in the SAP. For the ITT, respective restrictions will be applied as part of the first step in the EMA analysis (see Section 17.4.3).

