## 2.4. Open-Label Treatment Phase (Week 52 up to Week 104)

During the open-label treatment phase, three visits are scheduled in-clinic unless otherwise noted: Visit 8 at 56 weeks (telephone contact only for all but UK sites), Visit 9 at 78 weeks, and Visit 10 at 104 weeks. The last non-missing value/assessment prior to first dose of the open-label treatment phase serves as the Baseline visit for the open-label treatment phase, but subjects with a missing Week 52 efficacy endpoint are excluded from the respective non-inferiority PPv5-OL population (see Section 3.1.2).

Sponsor:	TauRx Therapeutics Ltd.		
Protocol:	TRx-237-039		
Document Version No.:	3.0	Document Date:	07-JUN-2023

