## Statistical Analysis Plan

Sponsor:	TauRx Therapeutics Ltd.		
Protocol:	TRx-237-039		
Document Version No.:	3.0	Document Date:	07-JUN-2023

---

subject to be excluded from the PP population. This file will include a description of the protocol deviation, will provide the information regarding previous classification (minor/major), will provide the classification into important/non-important done by the Sponsor, and will be finalized prior to unblinding of the double-blind treatment phase. The level of detail and information provided will allow full traceability.

All protocol deviations will be presented in a subject data listing (by Synteract, the vendor of the RAVE EDC clinical database; as well as via a Sponsor protocol deviation Log, which includes the manual generated protocol deviations that cannot be assigned to a specific subject data point). This listing will be presented pooled (COVID-19 and non-COVID-19 related protocol deviations) and separate for COVID-19- and non-COVID-19-related protocol deviations.

Summaries by categorization (important/non-important) and type (or code) will be provided by treatment phase. This will be done pooled and separate for COVID-19- and non-COVID-19-related protocol deviations. Also, one version will count all protocol deviations and one version will count only the overall unique deviations (when one deviation is resulting in subsequent ones).

Some examples for protocol deviations are:

- Protocol deviations related to Inclusion/Exclusion criteria (ineligible subject randomized to the study)
- Randomization/drug dispensation errors (incorrect kit dispensed to a subject)
- Use of “prohibited” concomitant treatments (e.g., AChEI or memantine)
- Non-compliance regarding study drug intake or endpoints assessment
- Baseline or Week 52 visit are not done in-clinic, but remotely
- Out of window assessments

Sponsor:	TauRx Therapeutics Ltd.		
Protocol:	TRx-237-039		
Document Version No.:	3.0	Document Date:	07-JUN-2023

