### **6.2. Open-Label Treatment Phase Definitions**

Based on the HMTM treatment history during the double-blind treatment phase “late” starters are defined as subjects originally randomized to control, and “early” starters are defined as subjects originally randomized to HMTM 16 mg/day or HMTM 8 mg/day. The last available assessment – for the scales: the last available (upscaled) value – prior to or on the same day of the start of the open-label treatment (Visit 7, Week 52) will serve as the Baseline assessment of the open-label treatment phase (Baseline-OL). A delayed performed Week 52 MRI assessment will be eligible for the Baseline-OL assessment if it has been done within 14 days after starting the open-label treatment phase.

The treatment group of subjects originally randomized to control will be labeled as “MTC 8 mg/week”.

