#### 6.10. Secondary Efficacy Endpoint Analysis

The goal of the open-label phase is to demonstrate disease modification by comparing the ADAS-cog11 change from Baseline-OL at Week 104 between early and later starters using a non-inferiority margin. According to the study protocol the non-inferiority margin will be set to 2 units, based on the estimated treatment effect of  $5.2 \pm 1.3$  (mean  $\pm$  standard error) units from a pooled analysis of the studies TRx-237-005 / TRx-237-015.

This non-inferiority margin, and the thresholds mentioned in Section 6.11, have been selected based on the results of the two previous phase 3 studies TRx-237-005, and TRx-237-015. It was planned to change the non-inferiority margin to 50% of the observed 52 treatment effect, should the decline and treatment effect for this study, seen after topline and full analysis of the double-blind treatment phase, deviate strongly from the expectations based on the TRx-237-005/TRx-237-015 results. With the knowledge of the double-blind treatment phase results, the non-inferiority margin will be as selected, based on the two previous phase 3 studies TRx-237-005, and TRx-237-015.

Efficacy analyses will be conducted using the PPv5-OL population (see Section 3.1.2) with no imputation of missing values. Upscaling for the scales will be performed. The ITTv5-OL population will be analyzed as a supplementary analysis and will include only those subjects with at least one post-Baseline-OL value.

The key secondary endpoint is the Baseline-OL adjusted decline in ADAS-cog11 from Baseline-OL at Week 104. Repeated measures on this endpoint scheduled at Week 78, and Week 104 will be treated using a mixed effects model. Suppose  $\mu_{\text{early}}$  and  $\mu_{\text{late}}$  are the corresponding means of decline at Week 104 for the early and late starters, then the null and alternative hypothesis can be written as:

$$H_0: \mu_{\text{early}} - \mu_{\text{late}} \geq 2; \text{ versus}$$

Sponsor:	TauRx Therapeutics Ltd.		
Protocol:	TRx-237-039		
Document Version No.:	3.0	Document Date:	07-JUN-2023

$H_1: \mu_{\text{early}} - \mu_{\text{late}} < 2$ .

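### The per-protocol set that decides the delayed-start test screens only open-label deviations, although the early/late contrast rests on double-blind exposure

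*SAP*

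**What the plan says.** HMTM in the SAP is LMTM in the protocol.

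- **The test.** SAP 6.10 compares early with late starters on ADAS-cog11 change from the open-label baseline at Week 104. The margin is 2 units and the one-sided level is 0.025. "Efficacy analyses will be conducted using the PPv5-OL population", while "The ITTv5-OL population will be analyzed as a supplementary analysis".
- **The labels.** Under SAP 6.2, late starters are those randomized to control; early "starters are defined as subjects originally randomized to HMTM 16 mg/day or HMTM 8 mg/day".
- **The set.** SAP 3.1.2 takes randomized subjects with at least one open-label dose and "without any important protocol deviation during the open-label treatment phase", and analyzes them by randomized group. The v5 set is the same, limited to subjects randomized under protocol version 5.0 or later.
- **Deviation examples.** SAP 3.2 lists "Randomization/drug dispensation errors (incorrect kit dispensed to a subject") and non-compliance with study drug.
- **Week 52 values.** SAP 2.4 states that "subjects with a missing Week 52 efficacy endpoint are excluded from the respective non-inferiority PPv5-OL population". It points to 3.1.2, which does not repeat the rule.
- **Protocol rule.** Protocol 17.3 defines its populations on the double-blind phase and says that the "population definitions will be used for the delayed-start analyses without any modifications". SAP section 10, on changes to planned analyses, does not mention the new set.
- **Trackers.** SAP 3.1.1 says that trackers from the blinded data review meeting (BDRM) and the open-label data review meeting will record exclusions, including those for PP-OL. No criterion there brings double-blind deviations into PP-OL.

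**The concern.** In the open-label year everyone on drug takes 16 mg/day. What separates early from late starters is what they took in the year before, and that is where a per-protocol screen for this comparison should look. As written, a subject can be removed from the double-blind PPv5 set for an exposure deviation and return as a per-protocol early or late starter.

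The direction matters because this is a non-inferiority test. An early starter who was effectively untreated in year one responds to the open-label drug as a late starter would. A late starter who received HMTM in year one behaves like an early starter. If late starters truly catch up, so that early minus late is positive, both kinds of subject shrink the difference toward 0 and make non-inferiority easier to declare. That result would support the disease-modification claim. The supplementary ITTv5-OL analysis does not help, because it keeps the same subjects and can add those who continued off treatment. The only listed sensitivity analysis (SAP 6.10.1) splits the early group by dose.

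**Working it through.** **Inputs.** Margin 2 and one-sided alpha 0.025 (SAP 6.10). SD 5.9, given in SAP 5.3 for the 52-week change and assumed here for Week 52 to 104. 160 to 170 per arm entering, then 10% dropout (SAP 6.4). Double-blind withdrawal 20% to 25% of 200 per arm (SAP 5.3). The share of PPv5-OL with altered double-blind exposure is not given, so it is varied.

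**1. The plan's power.** Power = Φ(2/SE − 1.96), with SE = 5.9·√(1/n₁ + 1/n₂) and true difference 0.

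- 200 × 0.75 × 0.90 = 135 per arm: SE 0.718, power 79.5%. This reproduces the stated 80%.
- 160 × 0.90 = 144 per arm: SE 0.695, power 82.0%.
- 170 × 0.90 = 153 per arm: SE 0.675, power 84.3%.

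A 20% to 25% loss from 200 leaves 150 to 160, not 160 to 170, so the 80% figure matches the lower end of the dropout assumptions rather than the stated entry numbers.

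**2. Error at the margin.** Let c be the sum of the early and late shares that behave exactly like the other group. If the true difference is 2, the expected difference is 2(1 − c), and the chance of declaring non-inferiority is Φ(2c/SE − 1.96).

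| c | 135 v 135 | 144 v 144 | 144 late v 180 pooled early |
|---|---|---|---|
| 0 | 2.5% | 2.5% | 2.5% |
| 5% | 3.4% | 3.5% | 3.5% |
| 10% | 4.6% | 4.7% | 4.9% |
| 20% | 8.0% | 8.3% | 8.8% |

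Example, 144 v 144 at c = 5%: 0.10/0.695 = 0.144, and Φ(0.144 − 1.96) = 3.5%.

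**3. Partial misexposure.** SAP 5.12.1 has one kit dispensed at each of four double-blind visits, so one wrong kit covers about a quarter of the year. Assume dilution in proportion to exposure, with 144 per arm.

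- 5% of early starters with one wrong kit in four: c = 1.25%, Φ(0.036 − 1.96) = 2.7%.
- 5% of early starters at half exposure: c = 2.5%, Φ(0.072 − 1.96) = 3.0%.

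**4. Other true differences.** At 0 there is nothing to dilute and no bias. If early starters do better, dilution pulls the estimate up toward 0 and works against non-inferiority. At 5.2, the pooled effect quoted in SAP 5.3, with c = 20% and 144 per arm, false non-inferiority stays below 0.0001%.

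**5. Power cost of screening.** From 144 per arm (82.0%), excluding 5%, 10% or 20% of subjects leaves 80.0%, 77.9% or 73.0%. From 135 per arm (79.5%), it leaves 77.5%, 75.2% or 70.2%.

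**The case against.** The strongest reply is that other rules already remove most of the worst cases. Several stronger readings fail on this.

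- **That barely treated subjects count as clean early starters.** Mostly they do not. PP-OL needs an open-label dose, and under SAP 6.1 subjects off treatment at Week 52 get none. Protocol 12.2.2 calls for discontinuation once interruption limits are exceeded. The remaining group is narrower and consists of early starters still on drug at Week 52: low compliers, for whom Protocol 12.6 provides re-education and then Medical Monitor contact; subjects who stopped on their own and resumed (SAP 4.4); and extended COVID-19 interruptions (SAP 2.5).
- **That every wrong kit or non-complier matters.** A swap between 8 and 16 mg leaves an early starter early, and a non-compliant control subject is still a late starter. Only control/HMTM crossovers and under-exposed early starters count.
- **That missing Week 52 values let year-one decline into the deciding test.** SAP 2.4 excludes those subjects from PPv5-OL. The fallback to an earlier value in SAP 6.2 can affect the supplementary set. What is left is a rule missing from 3.1.2.
- **That the protocol would have removed these subjects.** Protocol 17.3 carries over all its populations and does not make PP the delayed-start set. Protocol 17.4.6 builds on the MITT and ITT models, which do not exclude for kit errors or non-compliance. The departure is real and unlisted, but it does not show that the protocol prescribes this screen.
- **That the error rate is 8% or more.** That needs one subject in five to be wholly misexposed yet on drug at Week 52, and nothing in the documents supports such a rate.

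These points limit the size. They do not supply the missing screen.

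**Conclusion.** The gap stands as a definitional weakness, with an effect that is unknown and probably small. The deciding set has no criterion for double-blind exposure, although the contrast depends on it. The error figures hold only if the true difference is at the margin, the open-label SD is 5.9 and the misexposure is complete; with partial misexposure in 5% of early starters the error is about 2.7% to 3.0%. The documents give no deviation rate, so no particular inflation can be attributed to this trial. The unlisted departure from Protocol 17.3 and the mismatch between SAP 2.4 and 3.1.2 need reconciling whatever the size of the bias. This is a cheap improvement; it does not by itself invalidate the test.

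**What to change.** - In SAP 3.1.2, add to PPv5-OL a requirement of no important double-blind deviation affecting study drug exposure (a kit error crossing control and HMTM, or non-compliance), as flagged in the BDRM tracker. State whether prolonged interruption counts, since Protocol 12.6 assesses compliance after allowing for interruptions. Use the flags as they stood at the blinded review, because SAP section 10 records that version 3.0 followed partial unblinding.
- At minimum, prespecify that set as a sensitivity analysis in SAP 6.10.1.
- Do not require full PPv5 membership. Under SAP 3.1.1 that also needs valid post-baseline MRI data, and it could drop subjects for deviations unrelated to exposure.
- Repeat the Week 52 requirement of SAP 2.4 in 3.1.2, and list the departure from Protocol 17.3 in SAP section 10.

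The cost is some wording, one extra flag and a smaller set. Excluding 10% of 144 per arm costs about 4 points of power. The sensitivity-analysis route leaves the main test's power unchanged.

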### 3.1.3. HMTM Treatment Phase Population

**Safety HMTM (Safety-HMTM) Population:** all subjects with at least one dose of HMTM study drug. This means that control subjects (who received placebo and/or MTC 8 mg/week) not participating in the open-label treatment phase will be excluded. Subjects are analyzed as treated.

## 3.2. Protocol Deviations

The Sponsor, or designee, will be responsible for producing the final protocol deviations file and for determining what kind of deviations will be considered important and which of these require the

## Statistical Analysis Plan

Sponsor:	TauRx Therapeutics Ltd.		
Protocol:	TRx-237-039		
Document Version No.:	3.0	Document Date:	07-JUN-2023

---

subject to be excluded from the PP population. This file will include a description of the protocol deviation, will provide the information regarding previous classification (minor/major), will provide the classification into important/non-important done by the Sponsor, and will be finalized prior to unblinding of the double-blind treatment phase. The level of detail and information provided will allow full traceability.

All protocol deviations will be presented in a subject data listing (by Synteract, the vendor of the RAVE EDC clinical database; as well as via a Sponsor protocol deviation Log, which includes the manual generated protocol deviations that cannot be assigned to a specific subject data point). This listing will be presented pooled (COVID-19 and non-COVID-19 related protocol deviations) and separate for COVID-19- and non-COVID-19-related protocol deviations.

Summaries by categorization (important/non-important) and type (or code) will be provided by treatment phase. This will be done pooled and separate for COVID-19- and non-COVID-19-related protocol deviations. Also, one version will count all protocol deviations and one version will count only the overall unique deviations (when one deviation is resulting in subsequent ones).

Some examples for protocol deviations are:

- Protocol deviations related to Inclusion/Exclusion criteria (ineligible subject randomized to the study)
- Randomization/drug dispensation errors (incorrect kit dispensed to a subject)
- Use of “prohibited” concomitant treatments (e.g., AChEI or memantine)
- Non-compliance regarding study drug intake or endpoints assessment
- Baseline or Week 52 visit are not done in-clinic, but remotely
- Out of window assessments

Sponsor:	TauRx Therapeutics Ltd.		
Protocol:	TRx-237-039		
Document Version No.:	3.0	Document Date:	07-JUN-2023

